2.1 Primary Objective

- To assess the efficacy of rucaparib in patients with pancreatic carcinoma associated with a deleterious BRCA1/2 or PALB2 mutation by assessment of progression-free survival rate at 6 months (PFS6).

2.2 Secondary Objectives

- To evaluate efficacy by assessment of objective response rate (ORR) by RECIST v.1.1 in those with measurable disease
- To assess duration of response (DOR)
- To evaluate overall survival (OS)
- To evaluate the safety and tolerability of rucaparib

2.3 Exploratory Objectives

- To evaluate mechanisms of resistance to PARP inhibition by gene sequence and structural rearrangements of paired tumor samples and in circulating tumor DNA.
- To evaluate changes circulating tumor DNA (ctDNA) and in circulating tumor cells (CTCs) as a molecular marker of response

3 Investigational Plan

3.1 General Design

This is an open-label study of rucaparib in patients with locally advanced or metastatic pancreatic carcinoma and a known deleterious germline or somatic BRCA1/2 or PALB2 mutation.

3.1.1 Screening Phase

All patients will undergo screening assessments within 28 days prior to the first dose of rucaparib. AEs that occur after signing of the informed consent form and before administration of the first rucaparib dose will also be collected during this period.

Screening assessments will include demographics and medical history, prior treatments for pancreatic cancer (and other malignancies if applicable), prior and current medications and procedures, 12-lead electrocardiogram (ECG), ECOG performance status, hematology, serum chemistry, serum pregnancy for women of childbearing potential, urinalysis, physical examination, vital signs, weight and height measurements, adverse events, and radiological assessment by CT or magnetic resonance imaging (MRI). An optional tumor biopsy sample will be collected from patients who provide appropriate consent.

BRCA1/2 or PALB2 test results must be obtained for all patients prior to enrollment in order to confirm the mutation detected was classified as deleterious/pathogenic or suspected deleterious, or equivalent of either of these. *BRCA1/2 or PALB2* mutations in blood and tumor tissue samples may be collected for confirmatory analysis.

All patients who enroll on study must have a confirmed, deleterious/pathogenic or suspected deleterious or equivalent mutation in BRCA1, BRCA2 or PALB2. Mutations may be germline or somatic in origin and must have been identified by a CLIA certified laboratory from any of the following: blood, tumor tissue or circulating tumor material.

CONFIDENTIAL

This material is the property of the University of Pennsylvania.

3.1.2 Study Intervention Phase

All patients will have blood collected prior to treatment for storage. Archival tumor tissue samples, if available, will also be collected and stored. If considered safe and feasible, a tumor biopsy will be obtained prior to the first dose of rucaparib.

During the treatment phase (continuous 28 day cycles), patients will be monitored for safety and efficacy. Assessments during the treatment phase will include AEs, ECOG performance status, concomitant medications and procedures, physical examination, vital signs and weight measurements, hematology and serum chemistry, serum or urine pregnancy (per investigator discretion) for women of childbearing potential, CA 19-9 measurement, blood samples for circulating tumor material analyses and study drug administration and accountability. Patients will be assessed for disease status per RECIST v1.1 after every 2nd cycle of treatment, and then every 3rd cycle for patients who have been on the study drug for at least 2 years. Patients will continue to receive rucaparib until disease progression or other reason for treatment discontinuation.

Patients will be monitored continuously for safety. The Data and Safety Monitoring Committee (DMSC) of the University of Pennsylvania Clinical Trials Scientific Review and Monitoring Committee (CTSRMC) will evaluate safety and efficacy in compliance with a charter.

3.1.3 Treatment Discontinuation

Upon treatment discontinuation, all patients will return to the clinic for an End of Treatment (EOT) visit. Assessments at this visit will include AEs, ECOG performance status, concomitant medications and procedures, 12-lead ECG, physical examination, vital signs and weight measurements, hematology and serum chemistry, serum pregnancy for women of childbearing potential, CA 19-9 measurement, blood sample for circulating tumor material analyses, disease status assessment and study drug accountability.

In patients who discontinue treatment due to disease progression, a tumor biopsy will be collected if considered feasible and safe.

[figure not shown]
3.1.4 Follow Up Phase

All patients will have a 28-day follow-up period for AEs following the last dose of rucaparib. CT scans at 28-day follow-up should also be performed for patients who discontinued treatment for reason other than disease progression and did not have a radiologic assessment at the End of Treatment visit. After the 28-day follow-up visit, patients will be followed for survival every 8 weeks until death, loss to follow-up, withdrawal of consent, or study closure.

CONFIDENTIAL

This material is the property of the University of Pennsylvania.

3.1.5 Study Schema

3.1.6 End of Study

The trial will be completed when all enrolled patients have completed 6 cycles of treatment or have experienced progressive disease (PD), whichever occurs first.

3.2 Study Endpoints

3.2.1 Primary Study Endpoints

The primary study endpoint will be the PFS rate at 6 months (PFS6) as determined from a Kaplan-Meier curve. PFS defined as the time from start of study therapy to the occurrence of disease progression according to RECIST v1.1, as assessed by the investigator, or death from any cause. Patients who are alive and progression-free will be censored on the most recent date that documents progression-free status (i.e. scan date or clinic visit date).

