^m = Disease assessment to include clinical examination, and appropriate imaging techniques, including CT scans of the chest, abdomen and pelvis, with appropriate slice thickness per RECIST; other studies (MRI, X-ray, PET, and ultrasound) may be performed if required. The same method used to detect lesions at baseline are to be used to follow the same lesions throughout the clinical study. If a patient has known brain metastases, this disease should be evaluated at each required assessment.

ⁿ = Tumor scans to be performed within 7 days prior to start of every odd numbered cycle, ie prior to start of Cycle 3, Cycle 5, Cycle 7, etc. A confirmatory scan should be performed ≥ 4 weeks after an initial response of PR or CR is observed.

^o = End of treatment CT scans should be performed if treatment was discontinued for reason other than radiologic disease progression.

^p = If CT scans were not performed at End of Treatment or within 28 days prior to End of Treatment, a CT scan should be performed at the 28-day follow-up visit.

^q = Archival tumor tissue, if available, will be collected and stored. (Note: This sample is not required to be submitted on Cycle 1, Day 1, but should be submitted as soon as possible after a patient begins treatment with rucaparib).

^r = A screening tumor biopsy will be collected if deemed safe and feasible. A biopsy will be collected if the reason for discontinuation was radiologic disease progression.

CONFIDENTIAL

^s= All patients discontinued from treatment, regardless of reason, should be followed for survival every 8 weeks until death, loss to follow-up, withdrawal of consent from study, or closure of the study. Follow-up can be performed via telephone.

^t= Up to 50cc of whole blood to be collected in 4 total tubes, likely to include EDTA and Streck tubes. Refer to laboratory manual for details. *If a patient has been on for >12 cycles, stop collecting serial ctDNA until progression or concern for progression.

^u= Patients will have coagulation tests PT/PTT/INR in advance of the clinical trial biopsy

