8.1 Primary Endpoint

The primary study endpoint will be progression-free survival (PFS), defined as the time from start of study therapy to the occurrence of disease progression according to RECIST v1.1, as assessed by the investigator, or death from any cause. Patients who are alive and progression-free will be censored on the most recent date that documents progression-free status (ie., scan date or clinic visit date). The PFS6 will be estimated from the Kaplan-Meier curve.

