8.2 Secondary Endpoints

The secondary endpoints are:

- (1) Objective response will be scored per RECIST v.1.1 as assessed by radiology review.
- (2) Objective response rate (ORR) is defined as the proportion of patients who achieve a complete or partial response, as determined by RECIST v1.1.
- (3) Duration of response (DOR) is defined as the time from first documentation of complete or partial response by RECIST v.1.1 to date of disease progression or death due to any cause. Responders who have not progressed will be censored on the most recent date that documents progression-free status.
- (4) Overall survival (OS) is defined as the time from start of study therapy to death due to any cause. Patients who are alive will be censored on the most recent date of patient contact.
- (5) The incidence of adverse events (AEs), clinical laboratory abnormalities and dose modifications.

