8.4 Statistical Methods

Clinical Statistics: We plan to enroll 42 patients in a single-arm one-stage phase II design. Progression-free survival at 6 months (PFS6) will be the primary clinical outcome and it will be estimated using the Kaplan-Meier method. Based on prior research[1, 2, 21, 39] the null hypothesis is that the PFS6 rate in this population of subjects is 44%. The alternative hypothesis is that the PFS6 rate is 60%. Forty-two patients provide 81% power to detect this increase in PFS6, at a two-sided 5% significance level, assuming an exponential distribution and that enrollment will continue for 42 months with an additional 6 months of follow-up prior to the final statistical analysis. The confidence interval method will be used for the test of the primary hypothesis. A 2-sided 95% confidence interval for PFS6 will be constructed to determine whether the lower bound of this confidence interval excludes 44%, which is the historical control PFS6 rate. Secondary outcomes include overall survival (OS) and objective response rate (ORR); median OS and ORR will be estimated with 95% confidence intervals. Toxicities will be graded and tabulated and Grade 2 and Grade

CONFIDENTIAL

3 toxicity rates will be calculated. With 42 patients, we have 88% power to detect any toxicity occurring at a rate of 5% or more.

Translational Statistics: Genomic endpoints will also be assessed. Serial testing of the presence of mutations using tissue and peripheral blood will be described using graphical plots and descriptive statistics.

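### PFS can be censored at a clinic visit without imaging, so a patient who skips the week-24 scan and is never rescanned raises PFS6 slightly against the fixed 44%

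*Combined protocol and SAP*

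**What the plan says.** Section 3.2.1 defines PFS from start of therapy to RECIST v1.1 progression, as judged by the investigator, or death. Patients alive without progression are "censored on the most recent date that documents progression-free status (i.e. scan date or clinic visit date". Section 8.1 repeats the rule, again naming "scan date or clinic visit date".

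The DOR definitions in 3.2.2 and 8.2 are shorter. In 8.2: "Responders who have not progressed will be censored on the most recent date that documents progression-free status". Neither has the parenthesis naming a clinic visit.

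Footnote n of the schedule in section 6.1 sets imaging: "Tumor scans to be performed within 7 days prior to start of every odd numbered cycle". That places scans at about weeks 8, 16, 24 and 32. Clinic visits fall on Day 1 of every 28-day cycle.

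Section 8.4 reads PFS6 from the Kaplan-Meier curve and calls the trial positive if the lower limit of a two-sided 95% interval excludes 44%. The interval type is not stated. No section says how a missed or unreadable scan is handled.

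**The concern.** A clinic visit and a scan are treated as equal proof of no progression, but they cannot equally show progression. Appendix B (section 16.2) classes clinical decline without objective evidence as symptomatic deterioration. Apart from death and lesions measurable by caliper, a visit without imaging can add progression-free time but can hardly ever produce an event.

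The trial has one arm and a fixed benchmark, so no concurrent group shares the effect. Unverified time counts towards success on the primary endpoint.

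**Working it through.** **1. The plan's own figure.** Section 8.4 states "Forty-two patients provide 81% power to detect this increase in PFS6", "at a two-sided 5% significance level", for 44% versus 60%, exponential survival, 42 months of accrual and 6 of follow-up.
- Monthly hazards: −ln(0.44)/6 = 0.1368 and −ln(0.60)/6 = 0.0851; ratio 0.622.
- Expected events under the alternative: 42 × [1 − (e^(−6λ) − e^(−48λ))/(42λ)] = 35.1.
- Power: Φ(√35.1 × |ln 0.622| − 1.96) = Φ(0.853) = 80.3%. Testing S(6) with null and alternative variances gives 81.5%.

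The 81% reproduces. It does not depend on the censoring date, so the effect has to be sized separately.

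**2. Which dates matter.** Six months is about week 26, so PFS6 depends on the scans at weeks 8, 16 and 24, plus deaths. A visit between two scans that were both done changes nothing, because no progression is dated between them. The visit matters only if it passes a due scan that was skipped and no later scan follows.

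**3. Effect per patient.** Assume exponential PFS on this scan grid, no deaths among the affected patients, and missing unrelated to progression. Let q be the chance of staying clear from week 16 to week 24, and let k patients clear at week 16 skip the week-24 scan but be censored at a later visit. With S16 the week-16 estimate and n16 = 42 × S16 at risk, the excess is S16 × k(1 − q)/n16 = k(1 − q)/42.
- True PFS6 44%: q = 0.44^(1/3) = 0.7606, so 0.2394/42 = 0.57 point per patient. For k = 1, 2 and 4, PFS6 is 44.6%, 45.1% and 46.3%.
- True PFS6 60%: q = 0.60^(1/3) = 0.8434, so 0.1566/42 = 0.37 point per patient.

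Censoring at the week-16 scan leaves the estimate at 44.0% or 60.0% under these assumptions.

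**4. A borderline trial.** Take 42 patients with 6, 6 and 5 progressions at weeks 8, 16 and 24. Two others, clear at week 16, skip the week-24 scan, attend clinic afterwards and are never rescanned. The interval is linear Greenwood, SE = S × √Σ d/[r(r − d)].

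| Handling of the two patients | PFS6 | SE | Lower limit |
|---|---|---|---|
| As written (at risk 42, 36, 30) | 25/42 = 59.5% | 7.57 | 44.7%, passes |
| Censored at week-16 scan (42, 36, 28) | 30/42 × 23/28 = 58.7% | 7.71 | 43.6%, fails |
| Both had in fact progressed | 23/42 = 54.8% | 7.68 | 39.7%, fails |

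With one such patient, last-scan censoring still passes (44.1%). A log-log interval gives 43.2% at 25/42, so this example fails under either rule with that method.

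**5. Wider simulation.** True PFS6 is 44% under full scanning, with 4,000 trials per row. All missed-scan and leaving rates are assumptions.

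| Scans missed; leaving per cycle without a final scan | Visit date | Last scan |
|---|---|---|
| None; none | 44.0% | 44.0% |
| 10%; none | 45.7% | 45.6% |
| 10%; 3% | 45.6% | 45.3% |
| 20%; none | 47.7% | 47.6% |
| 20%; 5% | 47.6% | 46.5% |
| 20%; leaving 5 times likelier after unseen progression | 50.8% | 49.4% |

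The censoring rule alone adds 0.0 to 1.4 points. In the last row the false-positive rate (nominal 2.5%, linear interval) is 14.3% versus 11.1%. With 10% missed, 3% leaving and the end-of-treatment scan always done, the two rules differ by under 0.1 point.

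**The case against.** The protocol has real safeguards. Sections 3.1.4, 6.6, 6.7 and 7.8.1, and footnotes o and p in 6.1, ask for a scan at end of treatment or at the 28-day visit when treatment stops without radiologic progression. After that, follow-up is for survival only and may be by telephone (6.8), so no further scheduled visits extend PFS. Patients still on drug are due a week-32 scan. At even accrual of one patient a month, only about 7.4 − 6 = 1.4 patients would reach the analysis before that scan is due. Disease assessment includes clinical examination, so a visit-based rule is prespecified and defensible. All of this stands, and it keeps the likely effect small. It does not close the gap for an on-treatment patient whose scan is skipped or unreadable and never repeated. Section 6.9 also describes a withdrawing patient's final visit without listing a scan.

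Three stronger readings are tempting and not supported:
- A reader might infer that anyone who misses a scan is credited with extra time by this rule. It reaches only patients never found to have progressed. Progression first seen at week 32 is an event at that date under either rule, which is why the 20%-missed, nobody-leaving row shows 47.7% against 47.6%.
- A reader might infer that the error rate is materially inflated. With four such patients the one-sided error at 44% is 5.3% versus 2.8% (linear) or 2.6% versus 1.6% (log-log). But four would be about 16% of the roughly 24 patients clear at week 16, and nothing in the documents supports that rate.
- A reader might infer that DOR is censored at clinic visits too. Sections 3.2.2 and 8.2 do not say so; they leave the reference date open.

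**Conclusion.** The point holds in a limited form. The written rule accepts a visit without imaging as evidence of no progression, and any effect on PFS6 is upward. Its size is about 0.4 to 0.6 point for each patient who is clear at week 16, misses week 24, is seen in clinic and is not scanned again. This rests on exponential PFS, the 8-week scan grid and missing unrelated to progression. It is nil or negligible if due scans are done. The number of missed scans is not in the documents, so material bias is possible but not shown. Two such patients can decide a borderline result under a linear interval.

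Last-scan censoring should not be taken as a full cure. It leaves the inflation from progression first seen after a missed scan, and most of the inflation from dropout related to unseen progression (49.4% against a true 44% in the last simulated row). The change is worth making because it is cheap and removes a one-directional error from the primary endpoint of a single-arm trial.

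**What to change.** - In 3.2.1 and 8.1, censor at the date of the last evaluable RECIST v1.1 tumor assessment showing no progression, or at first dose if there is none. Section 8.5 already requires one post-treatment assessment for the efficacy population, so the fallback should rarely apply. Deaths still count as events.
- Keep the visit-date version as a sensitivity analysis.
- In 3.2.2 and 8.2, state the same reference date for DOR (last evaluable assessment without progression).
- Add a sensitivity analysis that counts patients without an evaluable week-24 assessment as PFS6 failures. It is deliberately severe and bounds what last-scan censoring cannot correct.

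Cost: a few sentences and no new data. The interval is slightly wider if scans are missed (SE 7.71 against 7.57 points in the example above). If scanning is complete, the result barely changes.

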3.2.2 Secondary Study Endpoints

The secondary endpoints include:

- Objective response will be scored per RECIST v.1.1 in those with measurable disease.
- Objective response rate (ORR) is defined as the proportion of patients who achieve a complete or partial response, as determined by RECIST v.1.1
- Duration of response (DOR) is defined as the time from first documentation of complete or partial response by RECIST v.1.1 to date of disease progression or death due to any cause. Responders who have not progressed will be censored on the most recent date that documents progression-free status.

CONFIDENTIAL

- Overall survival (OS) is defined as the time from start of study therapy to death due to any cause. Patients who are alive will be censored on the most recent date of patient contact.
- The incidence of adverse events (AEs), clinical laboratory abnormalities and dose modifications.

3.2.3 Exploratory Study Endpoints

The exploratory endpoints include:

- Gene sequence and structural rearrangements of tumor and circulating tumor DNA
- Circulating tumor material concentrations summarized over time
- Additional exploratory endpoints may be evaluated depending on sample availability and available technology.

4 Study Population and Duration of Participation

4.1 Inclusion Criteria

Eligible patients must meet the following inclusion criteria:

- Histologically or cytologically confirmed diagnosis of pancreatic carcinoma with locally advanced or metastatic disease
- ≥ 18 years of age.
- Eastern Cooperative Oncology (ECOG) performance status of 0 to 1.
- Patients may have previously failed non-platinum containing therapy or may never have previously progressed on treatment.
- Patients must be on treatment with platinum-based (cisplatin, oxaliplatin or carboplatin) treatment for locally advanced or metastatic pancreatic cancer and have received a minimum of 16 weeks of therapy without evidence of disease progression based on the investigator's opinion.
 - Discontinuation of the platinum component of the regimen for chemotherapy-related toxicity is permissible provided the patient has previously received at least 16 weeks of platinum-based therapy without evidence of disease progression ≤ 8 weeks after treatment with the platinum agent

Patients may have received <16 weeks of platinum therapy if platinum was not able to be used for medical reasons or was medically required to be discontinued for legitimate reason in the opinion of the investigator (ie allergy, intolerable organ dysfunction)

- Documented deleterious BRCA1/2 or PALB2 mutation (germline or somatic) as assessed by CLIA certified laboratory. Variants that are considered to be non-detrimental ("Variants of uncertain significance", "Variants of unknown significance", "Variant, favor polymorphism" or "benign polymorphism" etc) are not sufficient for study entry.
- Measurable disease is not required for enrollment.
- Adequate organ function confirmed by the following laboratory values obtained ≤ 7 days prior to the first day of rucaparib:
 - (1) Absolute neutrophil count (ANC) $\geq 1.0 \times 10^9/L$
 - (2) Platelets $>100 \times 10^9/L$
 - (3) Hemoglobin $\geq 9g/dL$
 - (4) Aspartate aminotransferase (AST) and alanine aminotransferase (ALT) $\leq 3 \times$ upper limit of normal (ULN)
 - (5) Total bilirubin $\leq 1.5 \times$ ULN; if liver metastases or metabolic disorder such as Gilbert's syndrome, then $\leq 2.5 \times$ ULN.
 - (6) Serum creatinine $\leq 1.5 \times$ ULN or estimated glomerular filtration rate (GFR) ≥ 45 mL/min using Cockcroft Gault formula.

4.2 Exclusion Criteria

Patients will be excluded from participation if any of the following criteria apply:

CONFIDENTIAL

- Prior treatment with a PARP inhibitor
- Patients who have demonstrated resistance to platinum agents (e.g. oxaliplatin, cisplatin) are not eligible to participate in this study
- Clinical evidence of uncontrolled malabsorption and/or any other gastrointestinal disorder or defect that would, in the opinion of the investigator, interfere with the absorption of rucaparib
- Acute infection requiring intravenous antibiotics, antiviral or antifungal agents during the 14 days prior to first dose of rucaparib
- Symptomatic or untreated CNS metastases.
- Expected life expectancy of <12 weeks as determined by the investigator.
- For fertile patient (female able to become pregnant or male able to father a child), refusal to use effective contraception during the period of the trial and for 6 months after the last dose of rucaparib for female patients and 3 months for partners of male patients.
- Received any systemic treatment for pancreatic cancer ≤14 days prior to first dose of rucaparib.
- Non-study related minor surgical procedure ≤5 days, or major surgical procedure ≤21 days, prior to the first dose of rucaparib; in all cases, patients must be sufficiently recovered and stable before treatment administration.
- Active drug or alcohol use or dependence that would interfere with study compliance.
- Presence of any other condition that may increase the risk associated with study participation or may interfere with the interpretation of study results, and, in the opinion of the investigator, would make the patient inappropriate for entry into the study.

